### Oculomotor Measures

Oculomotor control performance will also be compared using a 3 × 2 mixed-model ANOVA for each of the dependent variables. For smooth pursuit tracking performance, mean eye peak velocity and tracking lag will be submitted to separate 3 (group) × 2 (session) × 2 (random vs. sinusoidal task condition) mixed-model ANOVA.

## **(10) FACILITIES AND PERFORMANCE SITES:**

All MRI scanning will be performed on a 3 Tesla Philips Achieva MRI scanner located in Imaging Research Center (IRC) in the Cincinnati Children’s Hospital Research Foundation (CCHRf). Sedation will not be used for any of the test visits. The entire MRI series, including anatomical imaging, 3d T1, DTI, rs-fMRI, SWI, and HARDI will be completed in 60 minutes or less (see Table 1. below for detailed specifications). All functional and neurocognitive testing will be performed at the Cincinnati Children’s Hospital Human Performance Laboratory.

## **(11) POTENTIAL BENEFITS:**

Participants of this study will not receive any direct or immediate benefits by completing this study. However, they will be contributing to research involving the potential for major contributions to future TBI/concussion prevention strategies.

## **(12) POTENTIAL RISKS, DISCOMFORTS, INCONVENIENCES AND PRECAUTIONS:**

The Device partially circumnavigates and compresses the neck in the same way that a compression garment (non-medical apparel) behaves, and very similar to the compression exerted by a necktie (although this device is open over the trachea and can be pulled off if inadvertently gripped). These garments have been shown to gently facilitate natural response mechanisms in several small neck muscles and tendons (the Omohyoids), which are universally present in mammals and birds.

The physiologies imparted by these Omohyoids (and further facilitated by these garments) merely approximate natural physiologies, which occur when individuals lie in the prone, or supine position, and are also comparable to the simple act of yawning (which has been shown to collapse the jugulars). The Device will intentionally deliver an exacting, but gentle compression to the Omohyoid muscles in the neck allowing these muscles to optimize blood

outflow of the neck vasculature. In the upright position (without the collar), the resultant vascular blood column siphons volume out of the neck, rapidly, creating a negative pressure on the cranium and resulting in a slight “under filling” and “sloshability” inside the skull. The Omohyoid muscle raises the volume of the intracranial space by design. The Device does not contain any inherently rigid structures in its design. Similarly, neckties circumnavigate the neck, and safely raise intracranial pressure and volume comparable to the Device. The Device is manufactured of a soft rubber similar material and should be barely noticeable to the wearer. Careful MRI studies have confirmed an increase in blood volume in the brain but have also shown that there is no significant change in brain blood flow pattern with wearing a “tight necktie” (Rafferty 2010).

Although the venous jugular flow beneath the pressure cuff may be temporarily halted or slowed, the venous outflow from the cranium is never completely stopped, particularly from the anastomosis between the spinal vein and the basilar plexus and occipital sinuses *which are incompressible.*”(Gregg 1944) Jugular compression has few known physiological effects besides the intended increase in cerebral blood volume and pressure. Only one innocuous physiology has ever been shown to alter with jugular compression. “Previous studies have shown that the decline in urinary sodium excretion which occurs normally in the sitting position, as compared with recumbency, can be partially but not completely prevented by compression of the neck (Lewis 1950; Torres 1970). This decline in urinary sodium excretion is minimal. There was no correlation between EEG changes and changes in systolic blood pressure occurring during jugular or carotid compression(Torres 1970). Further, studies on complete resection of the IJV note that, “the clinical observation that bilateral resection of the IJV is usually well tolerated suggests the presence of alternative, non-jugular pathways.”(Gius 1950)

*Effect of Body Position and Exercise on ICP:* “At rest, compared with the reference 30-degree head-up position, the supine position increased intracranial pressure (ICP) by 6.21 mm Hg (35% with  $P < .01$ ).”(Brimiouille 1997) Restated, just lying down increases ICP more than the Device (6.21mm Hg = 35% rise versus this device at only 25%). *Valsalva and raising ICP:* We define Valsalva, where a person tries to exhale forcibly with a closed glottis (windpipe), so that no air goes out through the mouth or nose. “When the Valsalva maneuver was performed during resistance exercise, the ICP rose to 31 mmHg (a rise of 138%). No complications were associated with participating in this investigation.”(Haykowsky 2003) In other words, the Device facilitates the intended actions of the omohyoid with less pressure than the act of lying down or performing the Valsalva (holding one’s breath and bearing down, which would be expected to occur regularly on a playing field).

Instead of letting three to five milliliters of blood rapidly flow out of one’s brain upon standing, the Device will serve to retain that fluid inside the skull where it is believed to cushion the brain from external energy impacts and concussions. In rats, this simple action prevented 83% of TBI indicators during two 900 G impact studies at the West Virginia University.(Smith 2012; Turner 2012)Considering the above mentioned findings on jugular compression, this device can be considered not to meet the definition of a “significant risk device,” as that term is defined in 21 C.F.R. § 812.3(m).

***MR Imaging of the Brain:*** The risk the magnetic fields and the strengths, and radio waves is vanishingly small. Some patients can experience anxiety from the confined space of the magnet's bore. Therefore people with known claustrophobic tendencies will be excluded from the study. Another minor concern when using magnetic resonance technology is the noise the magnet makes when collecting data. Noise abatement measures are used; headphones and music with a selection of music options. Ferrous implants and or piercings can be affected in the magnetic field. Therefore participants will be advised to remove these and or scanned with a metal detector to screen for such objects.

Our colleague's previous experience with MRI experiments (who will be present and has a decade of experience with this technology) has provided confidence that there should be no psychological, physical, legal, or social risks involved with MRI experiments in general, though participants may be anxious about the scan, possibly causing them slight stress. The MRI scanning will be performed using the 3 T Siemens Trio MRI scanner. MRI does not involve ionizing radiation and scans up to 8 T are considered as non-significant risk. The risks common to all MRI scans can be described as: (1) ferromagnetic objects introduced into the magnetic field, (2) confinement in the scanner bore, (3) radio-frequency (RF) heat deposition in tissue which is monitored by the system to conform with FDA guidelines, and (4) acoustic noise. These risks are addressed below: Participants are allowed to communicate with the MR operator via an always-on, two-way intercom at any time. In addition, the participants have a hand-held air ball to squeeze in the event that they elect to be removed from the magnet immediately. Thus, the participants have control over their presence in the magnet, which in turn tends to minimize feelings of claustrophobia.

The MR imaging will be initially reviewed by a licensed radiologist just as it would be if it were being used as part of routine medical care. There is a possibility that while reviewing MR images we may see an abnormality that we did not expect to see in this study. In this event, we will notify the participant's legal representative (or participant is 18 years or older) if we see such an incidental finding. Depending on the type of incidental finding, we may contact the participant by mail or by phone. A member of the research team will discuss the incidental finding with the legal representative (or participant if over the age of 18 years). If the participant chooses, we will give information about this incidental finding to their primary doctor or we will refer them to an appropriate doctor for further evaluation. The costs for any care that will be needed to diagnose or treat an incidental finding would not be paid for by this research study.

***Data Storage.*** There is also a minimal risk that the data collected for each participant may be viewed by individuals outside the research team. The risk that confidential data may be viewed is relevant for both the written forms and electronic databases. Precautions, such as password-protected computers, locked cabinets and coded identification numbers, are in place to minimize this risk.

***Adverse Events.*** During the course of the investigation, injuries consistent with the sports being monitored are expected to occur (E.g. concussion, musculoskeletal injury, bone fractures). Care of all injuries will follow standard of care as directed by the team's athletic trainer and/or the participants treating physician. CCHMC will not be responsible for the

medical treatment of any injuries that are not directly related to wear of the Q-collar device. In the case of an adverse event that is determined to be directly related to the wear of the Q-collar during competitive play, the principal investigator will report such event to Cincinnati Children's Hospital Medical Center IRB as any future funding organizations in a manner consistent with the requirements of each organization. As described in the consent, if a participant believes they have sustained an injury as a result of the study then they are instructed to contact the principal investigator or director of social services who in turn will then contact CCHMC IRB and necessary funding institutions, as aforementioned. If a participant sustains an injury during testing they will be referred to the most appropriate medical facility or seek medical attention by the physician/medical specialist of their choice.

**(13) RISK/BENEFIT ANALYSIS:**

Participants will be approached for participation via the appropriate method. The purpose and the study protocol will be fully explained in conversation and with the informed consent process.

On the day of the study, the investigators will confirm that the volunteer participant has no health impairment as outlined in the exclusion criteria. Time will be taken to repeat the aims of the study, test protocol, and to answer any remaining questions posed by the participant. The methods described in this protocol have been used extensively in previous testing in the laboratory. During previous testing, there have been no reported injuries, adverse events or complications. Additionally, the investigators have considered potential risk for injury and have taken additional steps, described in the protocol, to minimize these risks.

A study participant may be withdrawn from the investigation if they demonstrate repeated alteration in their proper football tackling technique, such as adoption of spearing tackling tendencies. Subject participation will also be halted should an adverse event **while wearing the collar**, such as syncope, occur. Any adverse events will be immediately reported. The safety officer will evaluate all adverse events and will determine if early stopping of the study due to safety concerns is warranted. Given the study design and sample, we do not deem futility or efficacy stopping rules are warranted.

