**(5) DURATION:**

The study recruitment and intervention will occur during one season. Each participant will participate in 2 planned study visits that may take up to 2 hours. Data analysis will continue for a 2 year period following the final enrollment.

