**(6) SELECTION & RECRUITMENT OF PARTICIPANTS:**

The purpose of the present study is to generate pilot data for effect size estimation and power analysis for future study. The group size proposed in the aims was determined empirically based on previous neuroimaging studies and study designs reported in the literature. The sample size proposed in this pilot study will not warrant extensive statistical analysis to test the listed hypothesis. This study is expected to lead to an accurate estimate of effect size and variability so that future studies can be designed more rigorously.

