#### **(8) STUDY PROCEDURES:**

**Location I – Brain Imaging-Performed at CCHMC Imaging Research Center**

##### **MR imaging data Acquisition**

Magnetic Resonance Imaging (MRI), including sequences outlined in Table 1 are all based on the concept of using magnetic fields and radio waves to make chemical, anatomical and physiological assessments with in the living tissue. This technology has been utilized for diagnostic and research purposes since the early 1980s.

This testing will consist of a minimum of 2 MRI sessions (preseason, and post season) and additional scans following any clinically diagnosed concussions, all inside a 3T scanner at the CCHMC Imaging Research Center. During the acquisition of MR images, the study participants will lie on the scanner table. For most portions of MR acquisition, the study participants will only be instructed to lie still. For other parts of the acquisition, study participants will be asked to answer questions that will assess their cognitive ability and working memory. Participants will be allowed to communicate with the MR operator via an always-on, two-way intercom at any time. In addition, the participants have a hand-held air ball to squeeze in the event that they elect to be removed from the magnet immediately. The study participants have control over their presence in the magnet, which in turn tends to minimize feelings of claustrophobia. As magnetic resonance imaging employs the use of strong magnets, patients will receive a standard preoperative screening questionnaire regarding the potential for ferromagnetic objects within their bodies to ensure their safety during the study. Participants will be screened for MRI specific contraindications such as:

- Braces or permanent metal dental work
- Insulin pump
- Cardiac pacemaker
- Cochlear implants
- Hearing aids
- Aneurysm clips
- Orthopedic pins, wires, screws, or plates
- Any other exclusionary criteria as documented on the MRI safety screening poster included with recruitment materials

Those participants with any aforementioned contraindication will be excluded from the imaging portion of the study but will still be eligible to participate in the rest of the study procedures.

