**Statistical analyses.** - Statistical analysis of outcomes measures will be done using SAS®, version 9.3 (SAS Institute, Cary, NC) and SPSS statistical software (SPSS Inc, Chicago IL). Comparisons between the testing conditions (collar vs. no collar) will be made using Analysis of Covariance, in order to control for time (pre vs post season) and condition (collar versus no collar). We will also conduct correlation analysis to test the association between imaging biomarkers (as described above) with the results obtained from the impact surveillance. The collision indices,

including total number of collisions, number of collisions from front, back, left, right, top, bottom, G force, and timing of each collision will all be recorded and tested in the analysis. Secondary analysis to compare the intervention with no intervention and calculate the rates would involve a Poisson model, using an offset to account for the playing time and exposure to concussive impact for each of the study participants. We will calculate the rate and the associated 95% confidence interval. SAS®, PROC GENMOD will be used for analysis, which allows us to account for the fixed and random effects, use the appropriate link function, and the offset for amount of playing time exposure.

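### Section 13 halts study participation, not just collar wear, after an adverse event in the collar; read that way, post-season outcomes would be lost selectively in the collar arm

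*Combined protocol and SAP*

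**What the plan says.** Section 13 (Risk/Benefit Analysis) gives two rules in consecutive sentences. The first can apply to either arm: "A study participant may be withdrawn from the investigation if they demonstrate repeated alteration in their proper football tackling technique". The second begins "Subject participation will also be halted should an adverse event" and is triggered by an event that occurs while the collar is worn; syncope is the example given.

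Section 5 (Duration) describes participation in terms of the study visits: "Each participant will participate in 2 planned study visits that may take up to 2 hours". Section 2 sets the purpose as comparing pre- to post-season change between athletes with and without the device. Section 9 (Statistical analyses) states: "Comparisons between the testing conditions (collar vs. no collar) will be made using Analysis of Covariance". Section 6 gives the intended product of the pilot: "This study is expected to lead to an accurate estimate of effect size and variability".

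Section 6, and Section 8 (Injury Surveillance) for athletes with a concussion, also withdraw any athlete who stops playing the sport. Those rules apply to both arms.

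**The concern.** A precautionary rule that reaches only collar wearers is not a defect in itself. The difficulty is that this one appears to be tied to loss of outcome data. Its object is the subject's participation, not the device, and the word *also* links it to the withdrawal rule just before it. The protocol has wording for device use: Section 12 speaks of "medical treatment of any injuries that are not directly related to wear of the Q-collar device". Section 13 does not use such wording for what is halted.

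Every pre-to-post outcome needs the post-season visit. If a halted athlete misses that visit, collar-arm athletes who had an event in the collar drop out of the comparison, while similar control athletes stay in. Section 9 names no analysis set and no missing-data method for athletes without a post-season visit. The resulting estimate is the one meant to inform later trials.

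**Working it through.** **Reading the text**

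1. *Who can meet the trigger?* Only athletes assigned to the device. Sections 1 and 6 define the other group as wearing no device, and there is no sham.
2. *What is halted?* Participation by the subject. The link to the preceding withdrawal sentence, and the use of the word in Section 5, point to participation in the study.
3. *Does anything keep a halted athlete in follow-up?* Nothing visible in Sections 5, 6, 8, 9 or 13 does. The device and compliance paragraph in Section 8 (Injury Surveillance) is incomplete in the available text, so a definition there cannot be excluded.

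**Size**

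The plan gives no adverse-event rate, SD, effect size or dropout figure, so there is no planned figure to reproduce. Inputs:

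- n = 30 per arm. This is an assumption: Section 6 says up to 60 in total and gives no allocation ratio.
- SD of the pre-to-post change = 1 (scale), with no true collar effect.
- k = 0 to 3 collar athletes halted and not tested post-season (assumption).
- d = 0.25 to 0.5 SD, the difference in mean change between halted and remaining collar athletes, in either direction (assumption).

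If the remaining collar athletes have mean change m, the full arm has mean m + (k/30) × d. Analysing only those tested gives m. The absolute bias is therefore (k/30) × d. The standard error of the group difference is √(1/(30 − k) + 1/30).

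| k | Bias, d = 0.25 | Bias, d = 0.5 | Standard error | Increase |
|---|---|---|---|---|
| 0 | 0 | 0 | √(2/30) = 0.258 | – |
| 1 | 0.008 | 0.017 | 0.260 | 0.9% |
| 2 | 0.017 | 0.033 | 0.263 | 1.8% |
| 3 | 0.025 | 0.050 | 0.265 | 2.7% |

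At the largest, bias divided by standard error is 0.050/0.2653 = 0.19. If the halted athletes would have done worse, losing them flatters the collar; if better, it counts against the collar. If all halted athletes are tested post-season, the bias from this source is 0. Allocation by team, which Section 8 (Injury Surveillance) suggests, would change the standard errors but not the bias formula.

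**Cost of keeping them in**

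Suppose benefit is proportional to wear and k of 30 athletes stop halfway through the season. The estimated effect then shrinks by the fraction (k/30) × 0.5: 1.7% for k = 1 and 5% for k = 3.

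**The case against.** The strongest reply is that the plan never says a halted athlete misses the post-season visit. Where it means removal from the study it says withdrawn; here it says halted, which need not be permanent. Nor is participation a defined term: Sections 1 and 6 also use it for playing football. This stands in part. The data loss is an inference, and it is fair to say so. It does not remove the problem, because staff must act on the sentence as it is written and nothing visible tells them to keep testing.

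A second reply is that such events may not happen. Section 3 reports no statistically significant adverse effect in the athlete safety study and no untoward effects in 410 people tested with and without the collar. Section 13 reports no adverse events in previous laboratory testing. These were not full-season exposures, but they make zero events plausible, and the bias is then zero. This stands, and the range above starts at 0.

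A reader might go further and infer that every concussion or fracture sustained in the collar ends participation, since Section 12 lists such injuries under adverse events. The documents do not support that. Section 12 treats sport injuries as expected and separates them from collar-related ones. Section 8 plans "additional scans following any clinically diagnosed concussions", and its Injury Surveillance part plans a post-concussion battery. The reaction-time analysis in Section 9 has a concussion group, and Section 17 pays for post-concussion sessions. None of this is restricted by arm, so no bias figure built on losing collar-arm concussions belongs here.

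A reader might also infer that all attrition falls in the collar arm. It does not: the tackling rule and the stop-the-sport rules reach both arms.

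**Conclusion.** The point holds as a minor one, with medium confidence. As most naturally read, Section 13 ties a safety trigger that only the collar arm can meet to the end of study participation, so post-season outcomes would be lost selectively in that arm. On the assumptions stated, the bias is 0 to 0.05 SD, at most about a fifth of a standard error, with uncertain direction and little loss of precision. If the halt means only that the collar comes off, no data are lost through this rule and a clarifying sentence settles the matter. The documents do not support a claim that data will certainly be lost or that the comparison is seriously compromised. The case for acting is that the improvement is cheap and the pilot's purpose is to estimate an effect size.

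**What to change.** In Section 13, replace the halt of participation with a halt of collar wear on the same trigger; no judgement of relatedness is needed first. State that every halted athlete who still agrees completes the planned post-season testing and is analysed in the assigned group in the Section 9 collar versus no-collar comparison.

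Changing Section 13 alone would leave a gap. An athlete who faints in the collar and then gives up football would still be withdrawn under the stop-the-sport rule in Section 6, or under its counterpart in Section 8 (Injury Surveillance) if there was also a concussion. Add that an athlete who stops the sport after such an event is still invited to post-season testing, as an exception to those rules.

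The cost is a short amendment to Section 13 with a matching clause in Sections 6 and 8. It adds no visits, staff or procedures, because the post-season visit is already planned. Safety is not weakened, since the collar comes off on the same trigger. The downside is the slight dilution calculated above: about 1.7% to 5% if 1 to 3 of 30 stop at mid-season and any benefit is proportional to wear.
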